5.4.3.9.2. Analysis of Columbia Suicide ideation or behavior

Number (%) of subjects with suicidal ideation (overall and by category), suicidal behavior (overall and by category), suicidal ideation score ≥ 4 or suicidal behavior and/or self-injurious behavior without suicidal intent will be tabulated by treatment group at Core baseline visit and at Extension week 48. The "Lifetime" and "Recently" results will be summarized separately. In addition, the worst outcome of post-core-baseline assessment up to Extension EOT + 15 days (including the assessment at Extesion week 48) will be presented. Analyses will be based on subjects in the SAF and EXTS who have at least one eC-SSRS measurement during Combined analysis period available.

For subjects who have in addition a core baseline eC-SSRS assessment available shifts from core baseline (maximum score from pre-treatment recent history) to the worst reported outcome (the maximum score) up to Extension EOT + 15 days will be tabulated by treatment group to demonstrate any changes in Suicidal Ideation and Suicidal Behavior score categories (i.e. No ideation, non-serious suicidal ideation, serious suicidal ideation).

A listing will be generated for subjects who have positive value of any Suicidal Ideation, Suicidal Behavior or Self-Injurious Behavior without Suicidal Intent of that visits. To be specific, if a subject had outcome "Y" in the Suicidal ideation category "1-Wish to be Dead" at Extension visit 11, all suicidality scores of that visit will be listed. On the contrary, if all outcomes of suicidality score are negative then this visit won't be listed.

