1.1.1. Safety objectives and endpoints

- To describe the long-term safety and tolerability of ponesimod 20 mg in subjects with Relapsing Multiple Sclerosis (RMS).
- To describe the effects of re-initiation of ponesimod treatment after interruption in subjects with RMS.

Table 2 details the endpoints that will be analyzed for the Extension Analysis Period and for the Combined Analysis Period. See Section 5.1.5 for further details regarding the analysis strategy for safety.

Table 2: Safety endpoints

Endpoints	Combined Analysis Period	Extension Analysis Period
Adverse events		
• Treatment-emergent AEs, SAEs, and AESIs #	Y*	Y
AEs leading to premature discontinuation of study treatment	Y	Y
Cardiac safety		
• Treatment-emergent morphological ECG abnormalities (as defined by the ECG provider)	Y*	Y
 Absolute values by visit for 12-lead ECG parameters (HR, PR, QRS, QT, QTcB, QTcF) 	Y	Y
 Change from baseline values by visit for ECG parameters (HR, PR, QRS, QT, QT QTcB, QTcF) 	Y	Y
• Change in ECG parameters (HR, PR, QRS, QT, QT QTcB, QTcF) from predose to selected post-dose assessments (1 h, 2 h, 3 h, 4 h) on day of re-initiation of study treatment	N	Y

Pulmonary safety

Table 2: Safety endpoints

Endpoints	Combined Analysis Period	Extension Analysis Period
• Absolute values and percent change from baseline in FEV ₁ and FVC at all assessments	Y	Y
• Treatment-emergent decrease from baseline > 20% and >30% in FEV ₁ or FVC	Y*	Y
• Treatment-emergent decrease from baseline > 20 percentage points in % of predicted FEV ₁ and FVC	Y*	Y
• Change in lung diffusion capacity as assessed by DL _{CO} (at selected sites only) expressed in absolute change (mL) and % of predicted value from baseline at all assessments	Y	Y
Other endpoints		
• Absolute values and change from baseline for HR, SBP, DBP, and body weight at all assessments	Y	Y
Treatment-emergent notable blood pressure abnormalities	Y*	Y
• Absolute values and change from baseline for laboratory tests (hematology, blood chemistry) at all assessments	Y	Y
Treatment-emergent notable laboratory abnormalities	Y*	Y

^{*} Cumulative safety data, e.g., AEs for the combined Analysis Period will only be presented for subjects who received 20 mg ponesimod in the core study.

Analyses on the Combined Analysis Period use the core baseline as a reference, while analyses on the Extension Analysis Period use the extension baseline as a refence.

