5.1.5.2. Analysis strategy for safety

The long-term safety of ponesimod and the changes in safety in teriflunomide 14 mg subjects switching to ponesimod 20 mg will be investigated by summarizing the combined data from both the core and extension studies. Subjects will be analyzed according to the actual treatment they received in the core study (as derived in the core study ADaMs and not re-derived for the extension study analysis). Cumulative data such as AEs and SAEs will only be summarized for subjects initially treated with ponesimod 20 mg in the core study to allow a long-term assessment of up to 6 years. To assess trends over time and to assess the switch from teriflunomide 14 mg to ponesimod 20 mg, the analysis of the change from baseline for safety endpoints will be assessed by core study treatment group and by visit from core baseline up to last treatment + 15 days plus the EOS visit.

In addition, all safety data collected in the extension study will be analyzed for the extension study only and will summarize both overall and split by the core study treatment group. For this analysis, the extension study baseline is used as the reference.

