Furthermore, **self-injurious behavior without suicidal intent** is also an eC-SSRS outcome (although not suicide-related) and has a binary response (yes/no), this will be assigned as score 11 and to be summarized for subjects with these events.

The initial assessment has a lifetime and a recent history assessment. The recent history covers the last 1 month for suicidal ideation, and the last 3 months for suicidal behavior. Recent history questionnaire questions are only assessed for outcome categories with corresponding lifetime outcome question answered as yes. If the lifetime assessment for an outcome category is 'No', also the corresponding recent history outcome is considered 'No' for analysis. The "lifetime and a recent history assessment" is performed twice during the course of the study, respectively at core study baseline and at extension visit 7 – week 48.

Scoring: Scores are created at each assessment as follows:

- **Suicidal Ideation Score**: The maximum suicidal ideation category (1–5 on the eC-SSRS) present at the assessment. Assign a score of 0 if no ideation is present.
- **Suicidal Behavior Score:** The maximum suicidal behavior category (6–10 on the eC-SSRS) present at the assessment. Assign a score of 0 if no behavior is present.

For each assessment timepoint, a subject with multiple reported outcomes for suicidal ideation and suicidal behavior will be summarized under the worst reported outcome (i.e., max[1-5] and max[6-10], respectively).

Throughout all post-baseline assessments, a subject can have multiple suicidal ideation or suicidal behaviors, the worst reported outcome will be considered as the post-baseline outcome.

The following definitions will be used:

- Suicidal ideation: A "yes" answer to any one of the five suicidal ideation questions (Categories 1-5) on the eC-SSRS. Taken from the 'Reported most severe ideation level'.
- **Suicidal behavior**: A "yes" answer to any one of the five suicidal behavior questions (Categories 6-10) on the eC-SSRS.
- Suicidal ideation or suicidal behavior
- Serious suicidal ideation (score \geq 4) or suicidal behavior

The definitions above will be defined at any time in the period from study treatment start up to Extension EOT + 15 days*, for pre-treatment lifetime, and for pre-treatment recent history.

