Suicidal Ideation and Suicidal Behavior score categories: Shifts from baseline (worst outcome from pre-treatment recent history) to the worst outcome up to Extension EOT + 15 days (inclusive) will be derived using the following categories: No ideation (score 0), non-serious suicidal ideation (score 1-3), serious suicidal ideation (score 4-5), suicidal behavior (score 5-10).

*Only post-baseline assessments after study treatment start date from a 'since last call' questionnaires and the "Recently" questionnaire assessed at B303 extension week 48 (visit 7) are considered for the analysis.

Baseline is defined as last available recent history result (maximum score) up to study treatment start date at core study, i.e., pre-treatment recent history result at core baseline. This is taken from the answers to the "Recently" category questionnaires at core study baseline. If the lifetime assessment at core study baseline for an outcome category is 'No', also the corresponding recent

history outcome is considered 'No' for analysis. The core study baseline has already been derived and captured in B301 ADaM dataset and can be used directly.

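### The eC-SSRS plan has only a combined-period worst outcome and shift, so teriflunomide-to-ponesimod switchers get no cumulative on-ponesimod summary

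*SAP*

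**What the plan says.** The eC-SSRS text in the SAP uses one time window and one baseline.

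- Section 5.4.3.9.1, window: "The definitions above will be defined at any time in the period from study treatment start up to Extension EOT + 15 days".
- Section 5.4.3.9.1, baseline: "Baseline is defined as last available recent history result (maximum score) up to study treatment start date at core study". No extension baseline is defined for this instrument.
- Section 5.4.3.9.2, results: a table by treatment group at core baseline and at extension Week 48, with lifetime and recent answers kept apart; then "the worst outcome of post-core-baseline assessment up to Extension EOT + 15 days", with no grouping stated; then a shift from core baseline to the worst outcome "up to Extension EOT + 15 days will be tabulated by treatment group"; then a listing of visits with any positive answer.
- Section 5.4.3.9.2, population: "Analyses will be based on subjects in the SAF and EXTS who have at least one eC-SSRS measurement during Combined analysis period available".
- Table 6: eC-SSRS is marked for the combined period on the SAF. Its extension-period cell is empty, whereas exposure, adverse events, laboratory tests, vital signs, ECG and pulmonary safety are marked for both periods.

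The general safety rules are these.

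- Section 5.1.5.2: "all safety data collected in the extension study will be analyzed for the extension study only", overall and by core group, against the extension baseline. The same section limits cumulative combined-period data, with adverse events as its example, to subjects who started on ponesimod in the core study. Section 5.4.2.3 repeats both rules as the general approach.
- Section 5.1.2: by default, safety results are shown for both core groups and the total. For the combined period, exposure, the incidence of treatment-emergent events and adverse events are shown for the Ponesimod/Ponesimod group only.
- Sections 5.4.3.1.2, 5.4.3.2.2, 5.4.3.3.2 and 5.4.3.4.2 apply that restriction to the cumulative incidence tables for laboratory tests, blood pressure, ECG, spirometry and DLco.

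**The concern.** A worst outcome over a whole window is cumulative: one positive answer at any time fixes the subject's result. For a subject randomized to teriflunomide who then entered the extension, the window spans two drugs. A positive entry in the shift table could have arisen on either, and the table cannot say which.

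Section 5.1.5.2 sets out to describe the long-term safety of ponesimod and the change in safety when subjects switch to it. For suicidal ideation and behavior, no planned summary does the second for switchers on a cumulative basis. The other cumulative safety tables avoid the problem by restricting the combined period to core-ponesimod subjects and adding an extension-period version for everyone. The eC-SSRS section does neither.

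**Working it through.** The plan states no eC-SSRS figure to reproduce, so the check compares passages and adds two small calculations.

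**Step 1. What each planned output gives a switcher.**

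- *Week 48, lifetime answers:* reach back before ponesimod, so they are not an on-ponesimod result.
- *Week 48, recent answers:* cover the last month (ideation) or the last three months (behavior), as defined in Section 5.4.3.9.1. They fall on ponesimod but are a short look-back, not cumulative.
- *Worst outcome:* runs from core treatment start to extension EOT + 15 days. Under the default in Section 5.1.2, switchers appear with both phases pooled. If the table counts as treatment-emergent event incidence under the exception in Section 5.1.2, switchers do not appear at all.
- *Shift table:* same window, explicitly by treatment group, so both phases are pooled.
- *Listing:* identifies positive visits, so the study phase of each can be seen, but it has no denominators.

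None of these is a cumulative on-ponesimod summary for switchers. Naming the EXTS does not change this: the same sentence ties both sets to subjects "who have at least one eC-SSRS measurement during Combined analysis period available", so it alters who is counted, not the window.

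**Step 2. Share of a switcher's treatment time spent on teriflunomide.** Inputs: 108 weeks of core treatment (Section 1.2); 240 weeks of extension treatment, or 288 for Ukraine subjects (Sections 1.2.3 and 1.2.3.1). The gap between the studies is ignored. Formula: 108 / (108 + extension weeks).

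- Extension to Week 240: 108 / 348 = 31%.
- Extension to Week 288: 108 / 396 = 27%.
- Leaving at extension Week 48: 108 / 156 = 69%. The SAP does not say how many subjects do so.

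**Step 3. What an extension-only window could cover.** Table 12 schedules the eC-SSRS in the extension at Weeks 48, 96, 144, 192 and EOT, with none at Day 1. Section 5.4.3.9.1 admits only the recent answers at Week 48 and the *since last call* answers at other post-baseline assessments. Taking a month as 30.44 days, or 4.35 weeks:

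- Ideation: 48 − 4.35 = 43.65, so roughly extension Weeks 0 to 44 are not covered by the Week 48 answers.
- Behavior: 48 − 3 × 4.35 = 34.95, so roughly extension Weeks 0 to 35 are not covered.

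In a subject whose EOT comes before Week 48, the last call may have been in the core study. The *since last call* answer may then reach back to time on teriflunomide, even though it is dated in the extension.

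**The case against.** The strongest reply is that the eC-SSRS section is specific and may depart from general rules. Section 5.4.2.3 describes its approach as general, and Section 5.1.2 allows exceptions. The cumulative-data rule in Section 5.1.5.2 gives adverse events as its example, and whether a questionnaire maximum falls under it is a matter of interpretation. Section 5.1.5.2 also calls for change from baseline by core group to study the switch. The analyses are exploratory, and the positive visits are listed.

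Much of this stands, and it rules out several stronger inferences a reader might draw.

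- *That the Table 2 footnote is breached.* It says cumulative combined-period data "will only be presented for subjects who received 20 mg ponesimod in the core study", but it is attached to marked rows of Table 2, and eC-SSRS is not in that table.
- *That both tables merge the two drugs and contaminate a total column.* Only the shift table is explicitly by treatment group. The worst-outcome table has no stated grouping, and Section 5.1.2 may leave switchers out. The eC-SSRS section names no total column.
- *That about 31% of positive worst outcomes arose on teriflunomide.* The outcome is one maximum per subject, a subject may be positive in both phases, and capture is not proportional to time.
- *That about half of the extension set is affected.* Section 3 gives 1133 randomized and 877 enrolled, with no split by arm.
- *That a date filter alone yields a clean on-ponesimod result.* Step 3 shows that it does not.

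The reply does not remove the gap. The extension-only sentence in Section 5.1.5.2 is unqualified. The change from baseline described there is by visit, not a worst value over two treatments. If Section 5.1.5.2 is read as already requiring an extension analysis, then the eC-SSRS section and Table 6 fail to specify it.

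**Conclusion.** The concern holds in a limited form. On any reading of the eC-SSRS section as written, switchers have no cumulative on-ponesimod summary. That conflicts with Section 5.1.5.2 and is out of line with how the other cumulative safety tables are handled. The shift table pools up to 108 weeks of teriflunomide with ponesimod; for the worst-outcome table the treatment of switchers is unsettled.

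For scale, 31% of treatment time is on teriflunomide in a switcher followed to Week 240. This assumes full treatment in both studies and says nothing about events. The Ponesimod/Ponesimod group is not affected, apart from the gap between the studies. No hypothesis test is touched, since Section 2 specifies none. What is affected is the description of suicidality in switchers, which the document's own safety strategy calls for.

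**What to change.** 1. Add a worst-outcome table for the Extension Analysis Period on the EXTS, by core group and overall, built from extension assessments up to EOT + 15 days. Mark it in the extension column of Table 6.
2. Restrict the combined-period worst-outcome and shift tables to core-ponesimod subjects, or keep the switcher column and label it as covering both drugs. State the grouping of the worst-outcome table.
3. Reconcile the analysis sets: Section 5.4.3.9.2 names the SAF and the EXTS, while Table 6 marks only the SAF.
4. State the limits in a footnote. Week 48 contributes only the recent answers, so roughly extension Weeks 0 to 44 (ideation) or 0 to 35 (behavior) are not covered. *Since last call* answers at an EOT before Week 48 may reach back into the core study and should be flagged or shown separately.

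The cost is a SAP wording change, one additional table from data already collected, and a flag for early EOT answers. No new data are needed.

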5.5. Other Analyses

5.5.1. Pharmacokinetics

No Pharmacokinetics analysis is applied in this study.

5.5.2. Immunogenicity

Details of immunogenicity analyses conducted in this study are presented in Sections 6.11 for Covid-19

5.5.3. Pharmacodynamics

The pharmacodynamic (PD) marker evaluated in this study is Peripheral lymphocyte counts, which were measured as part of the clinical laboratory hematology tests.

To capture the abnormality in lymphocyte counts, among the treatment-emergent-flags abnormal values, the lowest lymphocyte counts through all post-baseline assessments are further categorized into the following categories. This will be done separately for combined period and for extension period.

- $< 0.2 \times 10^{9}/L$;
- $\geq 0.2 \times 10^{9}/L < 0.5 \times 10^{9}/L$;
- $> 0.5 \times 10^{9}/L < 0.8 \times 10^{9}/L$;
- $\geq 0.8 \times 10^{9}/L < 1.0 \times 10^{9}/L;$
- $> 1.0 \times 10^{9}$ L.

The following analyses will be conducted:

- Peripheral lymphocyte counts and the associated percentage change from core baseline by visit and by treatment group during combined period using SAF, along with a line graph to present the percent change from core baseline in peripheral lymphocyte counts by treatment group over visit. Note that only the following nominal visits will be visualized in the plot: Core period -- Baseline, Week 2, Week 4, Week 12, Week 24, Week 48, Week 72, Week 96, Week 108, D15 FU, D30 FU; Extension period -- Baseline, Week 2, Week 4, Week 12, Week 24, Week 48, Week 96, Week 144, Week 192, Week 240, Week 288, extension EOT, extension EOS.
- Peripheral lymphocyte counts and the associated percentage extension change from baseline by visit and by treatment group during extension period using EXTS, along with a line graph to present the percent change from core baseline in peripheral lymphocyte counts by treatment group over visit.
- Incidence of treatment-emergent marked abnormalities for blood lymphocyte counts for combined period using SAF and for extension period using EXTS.

In addition, to understand the change in lymphocyte counts after EOT, the following analyses will be done for subjects who continue any DMT after EOT date versus subjects who have no DMT after EOT date:

- Peripheral lymphocyte counts over the following visits: Core baseline, Extension Baseline, Extension EOT, Extension EOS visit and the change from Core baseline using EXTS.
- A line graph to present the percent change from core baseline in peripheral lymphocyte counts over the following visits: Core baseline, Extension Baseline, Extension EOT, Extension EOS.

Note that the group labels in this analysis are "Any DMT" and "No DMT", irrespective of the treatment group. Only subjects who have EOS visit and the EOS visit is at least 5 days after the EOT date are included in this analysis(refer to section 5.5.6 for more details)..

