5.1.3.2. Core Baseline

The **core baseline value** for efficacy is defined as the last non-missing value recorded before or on randomization in the core study for each endpoint and each subject individually.

The **core baseline value** for safety is defined as the last non-missing value recorded before the first study treatment administration in the core study for each endpoint and each subject individually.

These variables are used as derived in the core study and are not re-derived for the extension analysis.

On days where study drug is initiated or re-initiated, the pre-dose assessment for that day is defined as the last non-missing assessment prior to the study drug intake on that day. The pre-dose assessment on Day 1 of the Analysis Period (if available) is identical to the corresponding baseline for that Analysis Period. In case of (partially) missing assessment dates/times, or for assessments reported on Day 1 (or day of re-initiation) with recorded assessment time contradicting the time point label (e.g., pre-dose, 2 hours post-dose), the nominal visit and time point labels will be used to determine whether an assessment is considered for baseline (e.g., a blood pressure measurement with an assessment date on Day 1 but with a missing assessment time or an assessment time prior to the reported time of first study drug intake will not be considered for baseline if reported under the time point "2 hours post-dose" in the eCRF; however, it will be considered if reported as "Predose" in the eCRF).

Analysis over the Extension Analysis Period will use the **extension study baseline**, while analysis over the Combined Analysis Period will use the **core study baseline**.

Absolute change from baseline is defined as post-baseline value minus baseline value, i.e., a positive sign indicates an increase compared to baseline. A percentage change from baseline is defined as the absolute change from baseline divided by the baseline value (if the baseline value is > 0) and then multiplied by 100. Absolute and percent change from both core and extension baseline is calculated and stored for all continuous safety data.

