5.4.2.3. Analysis of safety variables

If not otherwise stated, only safety data considered treatment-emergent (up to 15 days after the last treatment administration) in the respective Analysis Period will be included in tables and figures. Additionally, non-treatment-emergent data at Core Day-15 follow-up, Core Day-30 follow-up and extension EOS visits may also be included in certain tables and figures. All safety data will be included in listings, with flags for safety data considered to be treatment-emergent to a specific Analysis Period.

Generally, safety data are presented as follows:

Safety data collected in the extension study will be analyzed based on the **Extension Analysis Period** using the EXTS and will be summarized for all subjects overall and split by core study treatment group. The analysis of change from baseline for safety endpoints assessed by visit will use the extension baseline as reference.

Furthermore, the long-term safety of ponesimod 20 mg and the changes in safety for teriflunomide 14 mg subjects switching to ponesimod 20 mg will be assessed by summarizing all data in the **Combined Analysis Period** using the SAF. Cumulative data such as AEs and SAEs will only be summarized for subjects initially treated with ponesimod 20 mg in the core study. Safety endpoints assessed by visit will be summarized by core study treatment group. Analysis of change from baseline for safety endpoints assessed by visit will use the core baseline as reference, unless otherwise specified.

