In general, local laboratory results with missing visits labels are not included in any summary tables. However, due to regional crisis or other reasons, Central lab testing was not available for some patients and the laboratory tests were performed only locally. Therefore, data from local laboratory might also be considered for summary tables. Below is the hierarchy of assigning laboratory data for a definite nominal visit.

- 1. For nominal laboratory visit listed in section 6.12 (as well as the additional safety visit at week 8, week 16 and week 20), if there is scheduled central laboratory data, the results from the central laboratory data at this nominal visit will be used.
- 2. If there is no available scheduled central laboratory data at this nominal visit, data from centrally assessed unscheduled laboratory data attached to this nominal visit will be considered.
- 3. If there is no available central laboratory data attach to this nominal visit (neither scheduled nor unscheduled assessments), data from the following sources will be considered, within the time window of the nominal visit (see Table 7 for the visit window).
 - a. Locally assessed laboratory data within the designated visit window;
 - b. Remapped premature EOT at this designated visit window.

In case there are multiple data within the same visit window, the record closest to the scheduled target day will be selected for summary statistics. In case there are two records with equal distance to schedule target day, the one occurs after target day will be used.

Figure 2: Flowchart of selecting laboratory data for nominal visit

CONFIDENTIAL – FOIA Exemptions Apply in U.S.

In addition, the following figures will be produced for lymphocyte counts, both for the Combined Analysis Period, by core study treatment, using SAF, and for the Extension Analysis Period, using the EXTS:

• Summary of mean percent change from baseline values (and their standard error) for lymphocyte counts by visit: mean plot starting with zero change at baseline.

The specified abnormal findings (i.e. any laboratory test result of exceeding/not meeting the thresholds for marked laboratory abnormality in Section 6.10) in safety laboratory hematology, clinical chemistry and other laboratory parameters planned per protocol are also presented in subject data listings, for Extension Analysis Period only.

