- A line graph to present the percent change from core baseline in PFT parameters over the following visits: Core baseline, Extension Baseline, Extension EOT, Extension EOS.

Note that the group labels in this analysis are "Any DMT" and "No DMT", irrespective of the treatment group. Only subjects who have EOS visit and the EOS visit is at least 5 days after the EOT date are included in this analysis (refer to section 5.5.6 for more details).

Spirometry (Pulmonary Function Tests) - DL_{CO}

The following summary displays are provided, by study treatment group, for the Combined Analysis Period (the summaries marked with § will include only the subjects who were initially treated with ponesimod 20 mg in the core study) on the DLco sub-study safety analysis set, and for the Extension Analysis Period on the DLco sub-study extension analysis set:

- Treatment-emergent Hemoglobin corrected DLco, percent predicted DLco and DLco including absolute and percent change from core baseline, as described in Section 5.4.3.4.1, are presented, by parameter and visit. Except for 'Baseline', only treatment-emergent results from nominal scheduled visits are included; premature EOT visit is mapped to a scheduled visit. These are summarized descriptively and mean absolute and percentage changes from baseline are also presented graphically with their standard error over time (plots starting with zero change at baseline).
- Number and percentage of subjects with any occasion of treatment-emergent low Hemoglobin corrected DLco, Percent predicted DLco, and DLco values as defined in Section v are presented. Percentages are based on the number of subjects with at least one treatment-emergent result available for the corresponding parameter.§

All notable abnormality DL_{CO} results (derived mean values per assessment) are listed by study treatment group and visit.

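### The extension-period lymphocyte graph and the DLco by-visit changes are tied to the core baseline, against the SAP's own rule for that period

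*SAP*

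**What the plan says.** The baseline rule for the Extension Analysis Period appears four times in the SAP:

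- Section 5.1.3.2: "Analysis over the Extension Analysis Period will use the extension study baseline".
- Section 1.1.1, note to Table 2: "analyses on the Extension Analysis Period use the extension baseline as a refence".
- Section 5.1.5.2, on the extension-only safety analysis: "For this analysis, the extension study baseline is used as the reference".
- Section 5.4.2.3, on by-visit safety data in the extension: "The analysis of change from baseline for safety endpoints assessed by visit will use the extension baseline as reference".

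In section 5.4.2.3 an allowance for exceptions is attached only to the sentence on the Combined Analysis Period. Appendix 2, which lists changes to the planned analyses, declares no exception for lymphocytes or DLco.

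Two outputs name a different reference:

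- **Lymphocytes, section 5.5.3, second bullet.** The table gives percentage change from the extension baseline, but the accompanying graph is set as "during extension period using EXTS, along with a line graph to present the percent change from core baseline in peripheral lymphocyte counts".
- **DLco, section 5.4.3.4.2.** The lead-in covers the Combined Analysis Period on the DLco safety set and the Extension Analysis Period on the DLco extension set. The first bullet then specifies "DLco including absolute and percent change from core baseline, as described in Section 5.4.3.4.1" without distinguishing the periods, and asks for plots that start at zero change.

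Section 5.4.3.1.2 also plans a lymphocyte figure for each period: "Summary of mean percent change from baseline values (and their standard error) for lymphocyte counts by visit: mean plot starting with zero change at baseline".

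**The concern.** A programmer following the specific bullets would break the general rule, and one following the general rule would depart from the bullets. The SAP does not say which prevails.

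For lymphocytes, one bullet gives a table and a graph with different references, and the SAP asks for two extension-period figures of the same marker on the same analysis set that would not agree.

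For DLco more is at stake. Table 2 lists DLco change as an endpoint for the Extension Analysis Period, and section 5.4.3.4.2 specifies no other by-visit DLco change summary. Taken literally, change from extension baseline would not be summarised by visit or plotted at all.

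**Working it through.** There is no design figure to reproduce. The check compares the texts and then works out how far the two references can differ.

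**Step 1. Reference named for each extension-period output**

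| Output | Section | Reference named | Agrees with the rule? |
|---|---|---|---|
| Lymphocyte percent-change table | 5.5.3, second bullet | extension | yes |
| Lymphocyte line graph | 5.5.3, second bullet | core | no |
| Lymphocyte mean plot | 5.4.3.1.2 | baseline, starting at zero; extension under the rule | yes |
| DLco by-visit changes and plots | 5.4.3.4.2, first bullet | core, for both periods | no |
| DLco incidence of low values | 5.4.3.4.2, second bullet | none named | no conflict |

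**Step 2. The zero starting point for DLco.** The by-visit list for the Extension Analysis Period in section 5.1.4 begins at the extension baseline. A core-referenced plot over those visits begins at the core-to-extension-baseline change, which is zero only if nothing changed. For the extension period, the DLco bullet therefore conflicts with its own plotting instruction as well as with the rule.

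**Step 3. Size of the difference.** For one subject, let c be the relative change from core baseline to extension baseline, and e the relative change from extension baseline to an extension visit.

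- Extension-referenced percent change: e
- Core-referenced percent change: (1 + c)(1 + e) - 1
- Difference: (1 + c)(1 + e) - 1 - e = c(1 + e)

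For absolute change, the difference is simply the absolute change between the two baselines.

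The SAP gives neither c nor e, so the values below are assumptions that show the range.

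| c | e | Core-referenced | Difference from e, c(1 + e) |
|---|---|---|---|
| -60% | -40% | 0.40 × 0.60 - 1 = -76% | -36 points |
| -40% | -40% | 0.60 × 0.60 - 1 = -64% | -24 points |
| -20% | -40% | 0.80 × 0.60 - 1 = -52% | -12 points |
| 0 | -40% | 1.00 × 0.60 - 1 = -40% | 0 |
| +10% | -40% | 1.10 × 0.60 - 1 = -34% | +6 points |
| -4% | -2% | 0.96 × 0.98 - 1 = -5.9% | -3.9 points |

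When e = 0 the core-referenced value equals c. For e above -100%, the two references agree only when c = 0.

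**Step 4. Effect on the group comparison.** Section 5.1.5.1, in setting the efficacy strategy, says the two core-treatment populations must be assumed to differ at extension start. If c differs between the groups, core-referenced extension curves are shifted by different amounts in the two groups.

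**The case against.** The best case for leaving the text alone is that little depends on it. The study is exploratory and tests no hypotheses (section 2). The extension lymphocyte table is correctly specified, and section 5.4.3.1.2 adds a by-visit percent-change table and a zero-start plot for the same period. Taken literally, the graph in section 5.5.3 is one extra figure, and no lymphocyte result is lost. For DLco, the zero-start instruction and the Table 2 note both suggest that a period-specific reference was intended. The section the bullet cites, 5.4.3.4.1, calculates changes from both baselines in its spirometry part and leaves the baseline unspecified in its DLco flags. All of this stands, and it limits the consequence. It does not resolve the DLco bullet, which names the core baseline expressly for both periods.

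Four stronger readings are tempting, and the SAP does not support them:

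- **The effect of switching from teriflunomide would be lost.** Sections 5.1.5.2 and 5.4.2.3 assign the switch assessment for safety endpoints to combined-period analyses from core baseline, and section 5.1.3.1 shows the extension baseline as a visit in those tables.
- **The extension DLco summary would merely duplicate the combined one.** The two use different analysis sets (sections 4.1.2 and 4.1.5).
- **The discrepancy equals the change between baselines.** That holds for absolute change. For percent change it is c(1 + e).
- **c is two years of teriflunomide effect.** It is a net change. Under section 5.1.3.1 the extension baseline may come from a follow-up visit after core treatment ended.

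The post-treatment Any DMT / No DMT displays also use change from core baseline, but they include core baseline as a visit and are not in error.

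**Conclusion.** The contradiction is real and confined to two places: the extension-period lymphocyte line graph, and the DLco by-visit change summaries and plots as they apply to the Extension Analysis Period. DLco matters more, because literal programming would leave a listed extension endpoint without any by-visit change from its required baseline. For lymphocytes the result is one figure that disagrees with its own table and with a parallel figure.

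The size in percent change is c(1 + e), which cannot be fixed from the SAP; the figures above are illustrations on assumed values. No test or error rate is affected, and the switch assessment does not depend on these displays. The conclusion assumes that the bullets would be programmed as written and that no exception to the general rule was intended, since none is declared. A possible cause is wording carried over from the combined-period lymphocyte bullet and from a DLco plan that, according to Appendix 2, first covered only the Combined Analysis Period. That is an inference. The correction should be made, but it is a modest one.

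**What to change.** 1. In the second bullet of section 5.5.3, change the reference of the line graph from core baseline to extension baseline.
2. In the first DLco bullet of section 5.4.3.4.2, write: change from core baseline (Combined Analysis Period) or extension baseline (Extension Analysis Period).

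If a core-referenced display was intended in either place, the SAP should state it as an exception, give the reason and label the output accordingly. For DLco the extension-referenced summary would still be needed alongside it to meet Table 2.

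The cost is two phrases. Section 5.1.3.2 already has absolute and percent changes from both baselines calculated and stored for all continuous safety data, so no new data or derivation is required.
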